# 9. MEASURES

Table 1 displays the guantitative data collection plan and details of measures. The neuropsychological battery has been shown to be reliable and valid. Based on our pilot, estimated completion time for the initial baseline assessment will be 1 hour with each follow-up session lasting approximately 50 minutes. **Qualitative assessment**: individual interviews will be conducted over the phone with members of the intervention group to understand the perceived facilitators and barriers to use of the intervention. All interviews will be conducted after the intervention, recorded digitally and labeled with a patient identification number. This will be done only one time and will last up to 30 minutes.

		No. li (Pote ran	tems/ ential ge)			
Variable	Instrument (Measure)	T1 T2		Instrument Range	Reliability	S c r e
	Screening					
Perceived Cognitive Function	Numeric rating scale (0 to 10)	Х		0-10	n/a	$\rightarrow$
Depression	PHQ-9 	Х			0.84	$\downarrow$
	Aim 1: Satisfaction an	d Accept	tability			
Satisfaction	Client Satisfaction Questionnaire		Х	8-32	0.90-0.94†	Î
Acceptability	Acceptability Scale		Х		NA	1
	Aim 2 Subjective Cognitive Measures					
Perceived Cognitive Function	IPROMIS – Applied Cognition- Abilities	X	x	33 (33-165)	0.97†	↑ ↓

#### Table 2. Schedule of Quantitative Measures

	IPROMIS - Applied Cognition Gen. Concerns 	х	X	34 (34-170)		
	Aim 4 Objective Cognitive Measures					
Memory	Rey Auditory-Verbal Learning Test 	Х	Х	15 words, 5 trials (0-75)		
	Rivermead Behavioral Memory Test 	х	х	N/A		
Speed of Processing	Symbol Digit	Х	Х	7-500ms	0.78*	↑ ↑
riocessing					0.60*	
					0.71-0.88	Ļ
Working	Wechsler Adult	Х	Х			
Memory	Intelligence Scale IV – Digit Span 					
Executive	Controlled Word	Х	Х	#words/1min	0.96	↑ (
Function -	Association 					
	Aim 3 Other				>.70	↑
	Outcomes					
Work Ability	Work Ability Index	Х	Х	7 (7-49)	0.98†	Ļ
					0.97†	Ļ
					0 99+	
Quality of Life	Quality of Life-Cancer	Х	Х	41 (0-10 on 4	0.66*	↓ ↑
	Survivors (QOL- CS) 			sub-scales)		
	Exploratory Aim 4 Intervention Effect on BDNF				0.93†	↑
Serum BDNF	Serum BDNF –ELISA			Х	Х	Assa
levels						ys
						: 7.8-
						500
	Intervention Fidelity		r –		Within accov	pg/ml
	Assessment & other				%CV at	1
	symptoms				334pg/ml =4.7%	
					Within assay	
					= 3.4%	
Dose	Time Spent each session	on – Com	nputer			N/A
Depressive	PROMIS-Depression	Х	Х	8 (0-40)		
Symptoms	Short Form 121 122	x	x	8 (0-40)		
Anxiety	PROMIS-Anxiety			0 (0 40)		
Fatigue	PROMIS-Fatigue	X	X	8 (0-40)		
	Short Form 	1	1	1		1

# 10. DATA ANALYSIS

Descriptive statistics and assessment of internal consistency reliability will be computed for all variables. Aim 1 Feasibility and Satisfaction: Descriptive statistics and frequencies will be used to summarize the Client Satisfaction Questionnaire and Acceptability Scale. The two groups will be compared on the mean of each item using the *t* test or Wilxocon rank sum test if the parametric assumptions are violated. Qualitative Analysis: A conventional content analysis approach, which aims to summarize the informational contents of the data, will be used. Common themes across all the participants' data will be identified and organized into clusters and categories. Aims 2-4: A linear mixed-effects models to analyze repeated-measures

ANCOVA, to compare the effects of cognitive training to attention control will be used. The dependent variables, cognitive performance measured post-intervention, will be the primary outcomes. The baseline cognitive performance will be adjusted for as a covariate. The other independent variables will be the fixed effect for training group (BrainHQ, attention control), the Time effect, and the interaction term of Time-by-Training Group. The primary test of interest will the Group effect, which compares the two randomized groups on the outcome. The second most important test will be the interaction test to determine whether change over time differs for the two groups. We will also assess the Time effect, which tests whether scores generally changed in one direction for both groups combined. In addition, to ensure equivalence across groups potential covariates will be adjusted for in the models on which the various intervention and control groups significantly differ after random assignment at a liberal p-value of <.10. Effect sizes between the two groups will be computed as differences between adjusted means divided by pooled standard deviations. The significance level will be <.05 for all tests of hypotheses. Aim 5 provides the estimation of the effect of cognitive training on serum BDNF. Similar to Aims 1 and 2, a GLMM will be fitted to the data to estimate this effect, while controlling for potential known confounding effects including, age, education, smoking status, body mass index, medications, physical activity (per DUKE Activity Status Index) that may influence BDNF interpretation prior to hypothesis testing; although the RCT design will likely balance these factors.

**Power analysis:** We are adequately powered for estimating effect sizes or preliminary efficacy (Aim 2). Sample size is based on Aim 2 preliminary tests of post-intervention efficacy of the intervention on continuous outcomes. A difference between means equal to 0.80 standard deviations represents a large effect size, a medium effect size is 0.50, and a small effect size is 0.20.96 Using the Nquery software, a sample size of 30 in each group will provide 86% power for a two-sided t test to detect a large effect size of 0.80 when alpha is .05, to detect small or medium effect sizes.

**Methods for Handling Missing Data and Dropouts:** The GLMM approach to analysis allows use of all available data, including from participants who have incomplete (i.e., partially missing) data. We will compare those who dropped out to those who completed the study on various demographic and treatment factors and on intervention group membership. To the extent that differences exist, we will describe this bias and its potential effects on the results of our analysis. Additionally, we will attempt to determine missing data patterns, and, if cell sizes permit, will incorporate this information into the analyses by re-running the GLMM with incorporation of the missing pattern as a nominal covariate.

Additionally, the influence of treatment dose (i.e.: sessions completed) will be evaluated to determine if it should be included as a covariate in the GLMM. Participants will be randomized only after completing baseline assessment. There are only two possible missing data patterns: baseline and immediate post only.

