# **1.1 Specific Aims and Hypotheses are:**

Aim 1: To evaluate the feasibility (including facilitators and barriers to use) and satisfaction of computerized cognitive training delivered in the home among BCS.

**Hypothesis 1**: BCS assigned to the cognitive training arm will perceive the intervention as more acceptable and useful than BCS assigned to the attention control condition.

Aim 2: To test the preliminary efficacy of the cognitive training intervention for improving perceived cognitive function over time compared to attention control.

**Hypothesis 2.1**: The intervention group will have greater improvement in subjectively measured cognitive function (Perceived cognitive impairment and Perceived cognitive capabilities) over time compared to attention control.

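### Hypothesis 1 is tested item by item at .05 with no decision rule, although the satisfaction total could serve as one deciding test

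*Combined protocol and SAP*

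**What the plan says.** Section 1.1 states Hypothesis 1 as one comparison between arms, with a direction: "BCS assigned to the cognitive training arm will perceive the intervention as more acceptable and useful than BCS assigned to the attention control condition".

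Section 10 handles Aim 1 in two steps. The first is descriptive: "Descriptive statistics and frequencies will be used to summarize the Client Satisfaction Questionnaire and Acceptability Scale". The second is the only inferential one: "The two groups will be compared on the mean of each item", using a t "test or Wilxocon rank sum test if the parametric assumptions are violated". Later in the same section the level is fixed: "The significance level will be <.05 for all tests of hypotheses". Section 10 names no lead item, no multiplicity adjustment and no count of items that would settle Hypothesis 1.

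The measures table in Section 9 lists two instruments for Aim 1, both collected only after the intervention. The "Client Satisfaction Questionnaire" has a score range of 8-32 and a reliability of 0.90-0.94, so the plan recognises a total score but never compares it between arms. The "Acceptability Scale" has no range, and its reliability is given as NA.

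**The concern.** One hypothesis is examined through a family of tests, and the plan does not say how their results combine into a verdict. Nothing in Section 10 rules out reading a single significant item as support. Under that reading the false-positive rate is well above the stated .05. If the sponsor instead corrects for the number of items, the analysis has less power than one test of a total score that is already collected.

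Aim 1 stands ahead of the aims that Section 1.1 labels secondary and exploratory, and the abstract says that positive results will lead to a full-scale trial. A claim that patients prefer the training programme should therefore rest on a rule fixed in advance.

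**Working it through.** **Inputs from the documents.** Satisfaction range 8-32 and reliability 0.90-0.94 (Section 9); two-sided .05 and 30 per arm (Section 10).

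**Assumptions.** There are k = 8 items, which fits a range of 8-32 if each is scored 1-4, but the item count is not stated. The reliability is internal consistency; its footnote mark is not explained in the available text. Items have equal correlations and, under the alternative, equal effects.

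**The plan's own figure.** Section 10 states that "a sample size of 30 in each group will provide 86% power for a two-sided t test to detect a large effect size of 0.80". With noncentrality 0.80 × √(30/2) = 3.10 and 58 degrees of freedom, the noncentral t gives 86.1%, so the figure reproduces. It was written for Aim 2; no power is given for Aim 1.

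**Correlation between items.** From reliability a = kr/(1 + (k − 1)r), r = a/(k − a(k − 1)):
- a = 0.90: 0.90/(8 − 6.30) = 0.53
- a = 0.94: 0.94/(8 − 6.58) = 0.66

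**False positives with no true difference.** Independent items would give 1 − 0.95^8 = 33.7%, an upper reference. Simulation of 40,000 trials with 30 per arm gave:

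| | r = 0.53 | r = 0.66 |
|---|---|---|
| At least one item significant, either direction | 24.1% | 20.8% |
| At least one item significant in favour of training | 12.1% | 10.4% |
| Either direction, items cut to four levels | 26.6% | 23.0% |
| One two-sided test of the total | 4.9% | 5.0% |

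For the total, half of 5%, or 2.5%, falls in the hypothesised direction.

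**Power.** The standardised difference on the total is the item difference times √(k/(1 + (k − 1)r)), which is 1.30 at r = 0.53 and 1.19 at r = 0.66. A total d of 0.80 then means an item d of 0.61-0.67; a total d of 0.50 means 0.38-0.42.

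| Rule, 30 per arm | Total d = 0.80 | Total d = 0.50 |
|---|---|---|
| One test of the total | 86% | 48% |
| At least one item, Bonferroni over 8 | 75-76% | 35-36% |
| At least one item, unadjusted | 95% | 71-72% |
| One item chosen in advance | 65-72% | 31-36% |

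Bonferroni is somewhat conservative here: its simulated error is 3.4-3.8%, because the items are correlated. Part of the power gap comes from that. The unadjusted any-item rule exceeds the total in power only because it runs at the 21-24% error rate shown above.

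**The case against.** The strongest reply is that Aim 1 is a feasibility aim in a preliminary trial. It leads with descriptive summaries and is supported by interviews; the sample size was set for Aim 2, and no efficacy conclusion depends on it. Item-level feedback is also useful for learning what participants liked. All of this stands and limits the importance of the point. It does not supply a decision rule for a hypothesis that the plan states and tests.

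A reader might infer stronger versions, which the documents do not support:

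- **That item testing both inflates error and loses power.** The two do not occur under one rule. If any significant item counts, error rises but power does not fall. If the item error is controlled, power falls but the inflation is gone. The 65-72% figure belongs to one item chosen in advance, a rule that the plan does not state.
- **That Hypothesis 1 would be falsely supported 21-24% of the time.** The hypothesis is directional, and only items favouring training support it. The relevant rate is 10-12%, against 2.5%.
- **That the Acceptability items push the error to a definite higher figure.** More items would raise it, but no item count is given, so any figure for both scales together is conjecture.
- **That both scale totals should be tested.** No range or reliability is given to support an Acceptability total. Two co-equal tests at .05 would also leave open which one decides.

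**Conclusion.** The point holds. Section 10 tests a single directional hypothesis through separate item comparisons at .05, without adjustment or a rule for combining them, and leaves the listed satisfaction total uncompared. If any significant satisfaction item counts as support, the chance of a false finding is about 21-24% in either direction and 10-12% in the supporting direction, against 5% and 2.5% for one test of the total. If the item error is controlled by Bonferroni instead, about 10 points of power are lost at a total d of 0.80 and about 12 at 0.50.

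The sizes rest on the assumptions set out above. The plan does not say that an any-item rule will be used; it fails to exclude one. The argument from a reliable total covers the satisfaction questionnaire only. Importance is moderate.

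**What to change.** In Section 10, under Aim 1:

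1. Make the comparison of the satisfaction total (8-32) between arms the single deciding test of Hypothesis 1, reported as a mean difference with a 95% confidence interval.
2. Report the Acceptability Scale as supportive. Use a scale score only if the internal-consistency check that Section 10 already plans for all variables supports one.
3. Present all item means descriptively, without p-values.

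The cost is one or two sentences, with no new data and no change to the sample size. Item-level p-values are given up, but item detail remains in the descriptive summaries and the interviews. Hypothesis 1 speaks of acceptability and usefulness, while the deciding instrument measures satisfaction. The sponsor should state that choice openly, since the satisfaction questionnaire is the only Aim 1 instrument with a documented score range and reliability.

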Specific aims are to: (1) examine the feasibility (facilitators and barriers) and satisfaction of the computer-based cognitive training program; (2) test the preliminary efficacy of cognitive training on improving cognitive performance (memory, processing speed, attention, working memory, executive function) over time compared to attention control; (3) evaluate cognitive training effects on associated outcomes compared to attention control; and (4) explore the effect of computerized cognitive training on serum brain derived neurotrophic factor (BDNF) over time compared to attention control. BDNF is widely distributed in the brain, plays a crucial role in neuroplasticity and has been observed to correlate with cognitive function in cancer patients. A total of 68 eligible BCS will be randomized to computerized cognitive training or attention control. A blinded and trained tester will perform data collection and neuropsychological testing at two time points: baseline prior to intervention (T1) and immediately after the 10-week cognitive training -program (within 90 days) (T2). Feasibility and satisfaction will be assessed through objective indicators (study adherence, completion rate) and self-report (facilitators, barriers, and perceived satisfaction) and cognitive performance will be assessed through objective neuropsychological tests of memory, processing speed, attention, working memory, executive function assessed over the phone. In addition, we will measure the effects of cognitive training on self-report measures of perceived cognitive function, associated symptoms (depressive symptoms, anxiety and fatigue), perceived work ability, and quality of life. Data will be analyzed using descriptive statistics and a general linear mixed model (GLMM). Simple main effects analyses will be used to follow up statistically significant interactions.

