Specific aims are to: (1) examine the feasibility (facilitators and barriers to use) and satisfaction of the computerized cognitive training program; (2) test the preliminary efficacy of cognitive training on improving objective cognitive performance over time compared to attention control; (3) evaluate cognitive training effects on associated outcomes over time compared to attention control and (4) explore the effect of computerized cognitive training on serum brain derived neurotrophic factor (BDNF) over time compared to attention control. A total of 68 eligible BCS will be randomized to cognitive training or attention control. A blinded and trained tester will perform data collection and neuropsychological testing at two time points: baseline prior to intervention (T1) and immediately after the 10-week cognitive training program (within 90 days) (T2). Feasibility and satisfaction will be assessed through objective indicators (study adherence, completion rate) and self-report and memory and speed of processing will be assessed through objective neuropsychological tests. In addition, we will measure the effects of cognitive training on self-report measures of perceived cognitive function, associated symptoms (depressive symptoms, anxiety and fatigue), perceived work ability, and quality of life.

**Innovatively, the proposed study builds on our pilot results and addresses limitations of previous trials including:** (1) uses home based training; (2) uses an attention control rather than a no-contact or wait-list control; (3) uses optimal intervention dose based on evidence, (4) explores cognitive training effects on real-life outcomes such as perceived cognitive impairment (using new PROMIS measures), associate symptoms, perceived work ability, and quality of life. This will also be the first study in the context of cancer to examine BDNF as a biomarker of intervention effects.

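### The protocol does not settle which outcome is primary: section 10 names cognitive performance, while section 1.1 and the measures table place objective performance in a secondary aim, and Aim 2, which sets the sample size, is defined in two ways.

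*Combined protocol and SAP*

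**What the plan says.** Section 10 (Data Analysis) is the only place that uses the term primary outcomes: "The dependent variables, cognitive performance measured post-intervention, will be the primary outcomes". The power paragraph of the same section adds: "Sample size is based on Aim 2 preliminary tests of post-intervention efficacy of the intervention on continuous outcomes". It names no instrument or domain, and states that "a sample size of 30 in each group will provide 86% power" for a two-sided t test at an effect of 0.80 SD and alpha .05.

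Elsewhere Aim 2 is defined in two ways:

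- **Objective.** The abstract's aim 2 is cognitive performance, and it explains that "cognitive performance will be assessed through objective neuropsychological tests of memory, processing speed, attention, working memory, executive function". The opening of section 1 gives aim 2 as: "test the preliminary efficacy of cognitive training on improving objective cognitive performance over time compared to attention control".
- **Perceived.** Section 1.1 defines Aim 2 as perceived cognitive function, with a hypothesis on subjective measures. The measures table in section 9 agrees and lists two PROMIS applied-cognition scales under Aim 2.

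Section 1.1 moves objective performance to Aim 4, below a heading for secondary and exploratory aims that begins at Aim 3. The measures table also lists the objective battery under Aim 4.

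**The concern.** A reader of section 10 would take objective test performance as the main efficacy result. A reader of section 1.1 would take self-reported function. The power statement attaches to one or the other depending on which numbering is followed.

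The two domains cannot stand in for each other. One is self-report by participants. The other is scored by the neuropsychological tester, the only party the protocol describes as blinded. The domains could give different answers, and nothing in the plan says which answer governs.

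The trial is framed as preliminary, which limits the harm. However, the abstract says positive results will lead to a full-scale study, and section 14 says that findings in either direction will guide clinicians and consumers. Whether the result is read as positive depends on the outcome taken as primary.

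**Working it through.** **1. The passages side by side**

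| Place | Aim 2 | Objective performance | BDNF |
|---|---|---|---|
| Abstract | objective | aim 2 | aim 4 |
| Section 1, opening | objective | aim 2 | aim 4 |
| Section 1.1 | perceived | Aim 4, secondary/exploratory heading | Aim 5 |
| Section 9, measures table | perceived | Aim 4 | exploratory Aim 4 |
| Section 10 | basis of sample size, not defined | the natural reading of the primary outcomes | Aim 5 |

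**2. Can section 10's own numbering settle it?** Only in part. "Aim 5 provides the estimation of the effect of cognitive training on serum BDNF" matches section 1.1. The next sentence, "Similar to Aims 1 and 2, a GLMM will be fitted to the data to estimate this effect", matches neither scheme: Aim 1 is feasibility and satisfaction in both, and section 10 analyses it by t test or rank-sum test.

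**3. The two readings**

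- Section 1.1 numbering: the powered outcome is perceived function, and the outcome called primary is objective performance. They differ.
- Abstract numbering: both are objective performance. They agree, but contradict section 1.1 and the measures table.

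Neither reading reconciles all the passages.

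**4. The stated power.** Inputs from section 10: n = 30 per group, d = 0.80, two-sided alpha .05. The noncentrality is d × √(n/2) = 0.80 × √15 = 3.098, with 58 degrees of freedom and critical value 2.002. Power from the noncentral t is **86.1%**, so the stated 86% reproduces. Because it is in SD units, the figure is the same for either domain.

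**5. Support for d = 0.80 in each domain.** Section 4 gives post-intervention pilot effects, against wait-list, of 0.75 for memory and 0.55 for processing speed. It gives no numerical effect for perceived function. With the same formula at 30 per group:

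- d = 0.75: noncentrality 2.905, power 81.5%
- d = 0.55: noncentrality 2.130, power 55.4%
- smallest d with 80% power: about 0.74
- d = 0.80 tested at .025 (critical value 2.301): power 78.5%

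These are unadjusted t tests. The planned baseline adjustment is not modelled.

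**6. Error rate if either domain could be called primary.** The plan says "The significance level will be <.05 for all tests of hypotheses". Take one endpoint per domain, each with critical value 1.96 and no true effect. The chance of at least one false positive favouring training is 1 − P(Z₁ < 1.96, Z₂ < 1.96), with Z₁ and Z₂ bivariate normal:

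| Correlation (assumed) | Favouring training | Two-sided |
|---|---|---|
| 0 | 1 − 0.975² = 4.9% | 1 − 0.95² = 9.8% |
| 0.7 | 1 − 0.9583 = 4.2% | 8.3% |
| Single prespecified endpoint | 2.5% | 5% |

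The protocol gives no correlation, so the range is an assumption. Multiplicity among several tests within one domain is a separate matter and is not counted.

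**The case against.** The strongest reply is that the sentence on primary outcomes is being read too firmly. It sits in a paragraph covering Aims 2 to 4, does not contain the word objective, and may be loose wording for the model's dependent variables. Section 10 also calls BDNF Aim 5, which suggests it follows section 1.1, so Aim 2 in the power paragraph most naturally means perceived function. Section 1.1 never uses the word primary. The error-rate range is hypothetical, since the plan lists two PROMIS scales and five objective tests rather than one endpoint per domain. The trial is preliminary, and both domains are collected in any case.

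Much of this is fair, but it does not remove the conflict. If section 10 follows section 1.1, the powered aim is perceived function while the outcome called primary is, on the usage elsewhere, objective performance; that is the contradiction itself. If cognitive performance is meant generically, up to seven measures become primary, each at .05, with no order among them. Aim 2's status in section 1.1 is indeed an inference from where the heading falls. No inference is needed to see that objective performance lies beneath that heading while section 10 appears to call it primary. What stands is that the error rates illustrate a possible risk and do not measure an effect of the conflict, and that the preliminary framing limits the consequence.

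**Conclusion.** The concern holds, and the text must be corrected. The primary efficacy outcome cannot be determined from the current protocol, and no reading makes sections 1, 1.1, 9 and 10 agree. The contradiction over Aim 2 is explicit. That section 10's primary outcomes are the objective tests rests on how the abstract, section 1 and section 1.1 use the term.

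The power arithmetic is not in error, and resolving the conflict does not by itself change 30 per group or 68 in total. What changes is the outcome to which the 86% applies and whether the protocol offers numerical support for the assumed effect. The possible inflation, about 1.7 to 2.4 percentage points above 2.5% in favour of training, depends on one endpoint per domain, free choice between them, and a correlation between 0 and 0.7.

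**What to change.** Before outcome data by arm are examined, amend the protocol as follows:

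1. Choose one domain as primary, and name one instrument or composite at T2. If perceived function is chosen, both PROMIS scales with a stated multiplicity rule would also serve. Label the other domain secondary.
2. Use one aim numbering in the abstract, sections 1 and 1.1, the measures table (including the BDNF row) and section 10 (including the comparison with Aims 1 and 2). Use the word primary in section 1.1.
3. State which outcome the 0.80 SD power statement refers to, and the basis for that effect.
4. If outcome data by arm have already been examined, say so in the amendment.

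The cost is an amendment. No new data are needed, because both domains are already measured at T1 and T2. The sponsor gives up the freedom to present the other domain as primary. Power remains 86% only if the chosen endpoint has an effect of 0.80 SD and is tested at .05; naming two PROMIS scales, each tested at .025, gives 78.5% per scale at that effect.

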#### Secondary and exploratory aims

**Aim 3:** To evaluate computerized cognitive training effects on secondary outcomes over time compared to attention control.

**Hypothesis 3**: The intervention group will demonstrate greater improvement in work ability, health perceptions, and quality of life over time compared to attention control.

Aim 4: To test the preliminary efficacy of the cognitive training intervention for improving objective cognitive performance over time compared to attention control.

**Hypothesis: 4**: The intervention group will have greater improvement in objectively measured cognitive function over time compared to attention control.

Aim 5 (exploratory): Explore the effect of computerized cognitive training on serum BDNF levels over time compared to attention control.

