Neuropsychological testing, completion of questionnaires and collection of a blood sample for BDNF will be collected at two time points during the study. Baseline (T1) data will be collected prior to the initiation of the intervention or attention control computerized training. Follow up assessments and BDNF blood sample will be collected post-intervention within 90 days of completing the intervention or attention control computerized training (T2)

Serum for BDNF analysis and all biomarkers that are part of this study will be prepared by laboratory services at IU and will be securely and confidentially (blood sample code) stored in the Analyte Laboratory within the Translation Core of the Center for Diabetes and Metabolic Disease under management of [name] (Co-I). The BDNF serum levels will be batch analyzed following collection of all samples following the manufacturers' ELISA protocol. The ELISA assay has standards ranging from 7.8 to 500 pg/ml BDNF (this is the possible range for all samples).

The study will also examine biomarkers that can affect brain functioning including neurotropic factor, proinflammatory cytokines, cortisol, and dehydroepiandrosterone (neuro steroid) DHEA.

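### Section 10 does not say that each outcome is adjusted for its own T1 value, BDNF included, and its Group, Time and interaction terms do not form a coherent model with only T1 and T2

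*Combined protocol and SAP*

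**What the plan says.** Section 10 (Data Analysis) describes a single linear mixed-effects model for Aims 2-4, labelled a repeated-measures "ANCOVA, to compare the effects of cognitive training to attention control will be used". Its response is given as follows: "The dependent variables, cognitive performance measured post-intervention, will be the primary outcomes". Its baseline term is given in the next sentence: "The baseline cognitive performance will be adjusted for as a covariate". The other terms are training group, "the Time effect, and the interaction term of Time-by-Training Group". The Group effect is ranked as the main test and the interaction second. Further covariates enter only if the arms differ on them after randomisation at p<.10.

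For Aim 5, a mixed model described as similar to Aims 1 and 2 is fitted to BDNF "while controlling for potential known confounding effects including, age, education, smoking status, body mass index, medications, physical activity". T1 BDNF is not in that list.

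The aims in section 1.1 are different constructs. Aim 2 is "To test the preliminary efficacy of the cognitive training intervention for improving perceived cognitive function over time compared to attention control". Hypothesis 3 is "The intervention group will demonstrate greater improvement in work ability, health perceptions, and quality of life over time compared to attention control". Objective performance appears as Aim 4, in section 1.1 and again in Table 2. Section 8.1 says that the T1 values will exist: "Neuropsychological testing, completion of questionnaires and collection of a blood sample for BDNF will be collected at two time points during the study".

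**The concern.** In a two-arm trial of this size, the T1 value of the same outcome is usually the best available source of precision. It also removes the effect of a chance T1 difference between arms. The plan names it only for cognitive performance. An analyst who follows the sentence literally for the PROMIS scales, the Work Ability Index or the quality-of-life scale would adjust for an objective test instead, and would have to choose which one. Aim 2, on which the sample size is based, is among the outcomes affected.

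The second difficulty is the set of terms. The response is described as post-intervention and T1 as a covariate, yet the model contains Time and Time-by-Group. With one post-baseline assessment these descriptions do not fit together, so the text does not determine which contrast would be reported as the main result.

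**Working it through.** **Inputs from section 10:** 30 per group, two-sided alpha .05, effect 0.80 SD, stated power 86%, t test. **Assumed, not in the documents:** T1-T2 correlation r of the same outcome, shown from 0.3 to 0.8; correlation of T1 objective performance with a T2 self-report score, 0.1 to 0.3.

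**1. The plan's own figure.** Noncentral t, 58 df, noncentrality d x sqrt(n/2) = 0.80 x sqrt(15) = 3.10. Power is 86.1%, which agrees with the stated 86%. No baseline adjustment enters it. At 0.50 SD the same test has 47.8%.

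**2. Own-T1 adjustment.** Residual variance is multiplied by 1 - r², so the standardised effect becomes d / sqrt(1 - r²), with 57 df. For r = 0.5: 0.50 / sqrt(0.75) = 0.577, power 59.4%.

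**3. Change test.** If T1 is in the response, the Time-by-Group test compares changes, whose variance factor is 2(1 - r). For r = 0.7: 0.50 / sqrt(0.6) = 0.645, power 69.1%.

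| r | Variance factor, own T1 | Power at 0.50 SD, own T1 | Power at 0.50 SD, change test | Effect detectable with 86% power, own T1 |
|---|---|---|---|---|
| 0.3 | 0.91 | 51% | 36% | 0.76 SD |
| 0.5 | 0.75 | 59% | 48% | 0.69 SD |
| 0.7 | 0.51 | 76% | 69% | 0.57 SD |
| 0.8 | 0.36 | 89% | 85% | 0.48 SD |

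The unadjusted T2 comparison gives 48% and 0.80 SD throughout.

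**4. A different T1 variable as covariate.** With a correlation of 0.1, 0.2 or 0.3 to the T2 outcome, power at 0.50 SD is 48.1%, 49.3% or 51.4%. Almost nothing is recovered.

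**5. Coherence of the terms.**
- *T2 is the only response.* Each woman contributes one value at one time, so Time and Time-by-Group have nothing to be estimated from.
- *T1 and T2 are both in the response.* Randomisation makes the expected T1 difference zero, so a Group main effect averaged over the two times has expectation (0 + d) / 2. A 0.50 SD effect at T2 appears as 0.25 SD. T1 would also be serving as response and covariate at once for any outcome adjusted for itself.

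**6. The p<.10 rule.** The standard error of a T1 difference is sqrt(2/30) = 0.258 SD. A difference must exceed about 1.67 x 0.258 = 0.43 SD to trigger adjustment. A one-standard-error imbalance (p about .32) does not, yet without own-T1 adjustment it moves the T2 difference by r x 0.258, which is 0.13 SD at r = 0.5 and 0.21 SD at r = 0.8.

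**The case against.** A reader might infer that perceived cognition, work ability, quality of life and BDNF will definitely not be adjusted for their own T1 values. The documents do not support that.

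- The response and covariate sentences in section 10 are a matched pair. If cognitive performance stands for every Aim 2-4 outcome in the first, it can do so in the second, and each outcome then gets its own T1. The abstract and the opening of section 1 still give objective performance as Aim 2, so section 10 may simply not have been updated to section 1.1.
- The Aim 5 variables are introduced as confounders, not as the whole model. The reference to Aim 2 may carry a baseline term across, although Aim 1 has no mixed model and Aim 2's only named covariate is cognitive performance.
- The interaction test, and the statement under missing data that the mixed model uses partially observed records, suggest that T1 is in the response. The interaction would then use each outcome's own T1. At r = 0.7 to 0.8 own-T1 adjustment gains only about 4 to 7 points over that test.

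These arguments stand against a proven omission. They do not settle the specification. The template reading is nowhere stated. The interaction is ranked second, and at r = 0.5 or below it is no better than the unadjusted comparison. The first-ranked Group effect is unadjusted for own T1 on the literal T2-only reading and diluted on the other.

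**Conclusion.** The point holds as a defect of specification. Section 10 does not state own-T1 adjustment outcome by outcome, the one baseline covariate it names belongs to Aim 4, T1 BDNF is not listed for Aim 5, and the stated terms cannot all be used sensibly with only T1 and T2. It does not follow that the sponsor intends to leave own-T1 adjustment out.

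If it were left out, the loss at 30 per arm and 0.50 SD would be about 4 points of power at r = 0.3, 12 at r = 0.5, 28 at r = 0.7 and 41 at r = 0.8, relative to an unadjusted T2 comparison. These sizes rest wholly on the assumed r. The sample size justification is untouched, because its 86% does not rely on adjustment. The point applies whichever outcome is treated as primary.

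**What to change.** Replace the response, covariate and model-term sentences in section 10 together, for example:

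> *For every outcome in Aims 2-5, the T2 value will be modelled on training group and the T1 value of that same outcome. The primary test is the adjusted group difference at T2.*

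Spell out the pairs: each PROMIS cognition scale, the Work Ability Index, each quality-of-life subscale, each cognitive test, and serum BDNF. Delete the Time and Time-by-Group terms and their tests. Changing the covariate sentence alone would leave terms that a T2-only model cannot estimate.

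An equivalent option is a constrained longitudinal model: T1 and T2 both in the response, a common T1 mean for the two arms, and the group contrast at T2 as the primary test. It keeps the mixed-model framework on which the missing-data paragraph relies.

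The six Aim 5 confounders may stay, provided that T1 BDNF is added.

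The cost is wording and one degree of freedom per model. No new data, participants or visits are needed. If own-T1 adjustment was always intended, that part of the edit only records it.
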